2.5. Primary Endpoint

The primary endpoint is a composite clinical endpoint constructed as a win ratio, a hierarchy of the following, which are assessed at hospital discharge or at 7 days after the index procedure, whichever is sooner:

1. All-cause mortality, or
2. Intracranial hemorrhage (ICH), or
3. Major bleeding per ISTH³ definition, or

PROPRIETARY AND CONFIDENTIAL

The information contained in this document is the sole property of Inari Medical

	PEERLESS Study: Statistical Analysis Plan	Version 5.0 March 22, 2024 Page 13 of 25
---	--	--

4. Clinical deterioration defined by hemodynamic or respiratory worsening, and/or escalation to a bailout therapy, or
5. ICU admission and post-procedure ICU length of stay

The first four endpoint events will be adjudicated by Clinical Events Committee (CEC). The definition of these endpoints can be found in the study protocol.

2.6. Secondary Endpoints

The secondary endpoints of the study will assess safety, effectiveness, and utility measures, as follows:

- Composite clinical endpoint constructed as a win ratio hierarchy of the following four components, assessed at hospital discharge or at 7 days after the index procedure, whichever is sooner:
 - All-cause mortality, or
 - Intracranial hemorrhage (ICH), or
 - Major bleeding per ISTH³ definition, or
 - Clinical deterioration defined by hemodynamic or respiratory worsening, and/or escalation to a bailout therapy
- Individual components of the win ratio composite endpoint, assessed at hospital discharge or at 7 days after the index procedure, whichever is sooner:
 - All-cause mortality
 - Intracranial hemorrhage (ICH)
 - Major bleeding per ISTH³ definition
 - Clinical deterioration defined by hemodynamic or respiratory worsening, and/or escalation to a bailout therapy
 - ICU admission and post index procedure ICU length of stay
- All-cause mortality within 30 days from index procedure
- PE-related and all-cause readmission within 30 days from index procedure
- Device and drug-related serious adverse events through the 30 day visit
- Clinically Relevant Non-Major (CRNM) and Minor bleeding events through hospital discharge or at 7 days after the index procedure, whichever is sooner
- Change in core-lab-adjudicated right-ventricular/left-ventricular (RV/LV) ratio from baseline to 24 hour visit, as measured by echocardiography or CT
- mMRC Dyspnea score at 24 hour visit and 30 day visit
- Length of post-index-procedure hospital stay (to a maximum of 30 days)
- Disease-specific and general health-related quality of life at the 30 day visit (PEmb-QoL and EQ-5D-5L)

PROPRIETARY AND CONFIDENTIAL

The information contained in this document is the sole property of Inari Medical

	PEERLESS Study: Statistical Analysis Plan	Version 5.0 March 22, 2024 Page 14 of 25
---	--	--

3. Analysis Populations

The analysis populations are defined as follows.

3.1. Intention To Treat Population

All subjects who met the inclusion/exclusion criteria, provided informed consent, and who were randomized to the FlowTriever or CDT group will be included in ITT. To be included in ITT, subjects must receive some treatment for PE after randomization. This study will consist of up to 550 subjects with acute PE who meet the eligibility criteria, and are enrolled, consented, and randomized. Subjects will be excluded from ITT population if no treatments were given, or no data were available after randomization.

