^f Imaging can be either echo or CT, but needs to be the same modality within each patient at Baseline and 24-hour visit

^g Note that the evaluation of endpoint considerations include All-cause mortality, ICH, Major bleeding, Clinical deterioration and/or escalation to a bailout therapy, and ICU admission and ICU length-of-stay. These are assessed at hospital discharge or 7 days after the index procedure, whichever is earlier. If a subject is still in the hospital and exits the study for any reason before the 30-day Visit, evaluation of primary endpoint components should be completed at the time of patient exit.

^h The Index Procedure begins when access for treatment is obtained. The Index Procedure is considered complete upon exit from the procedure room. The time of exit from the procedure room is the time reference used for the subsequent visit windows including the 24-hour visit.

BASELINE ASSESSMENTS

The baseline assessments must be done \leq 72 hours of Index Procedure including:

- Informed consent
- Inclusion/exclusion review
- Demographics
- Medical history, risk factors, and PE condition
- Anticoagulation regimen
- Clinical labs (Hemoglobin, Troponin)
- Cardiac imaging (Echo or CT)
 - Imaging can be either echo or CT, but needs to be the same modality within each patient at baseline and 24-hour visit.
- mMRC dyspnea score, Borg, and NYHA

ALLOCATION AND RANDOMIZATION

Upon the patient meeting baseline eligibility criteria and providing informed consent, a check against the list of absolute contraindications to thrombolytics is performed (see Figure 9: Patient Enrollment Flowchart). Subjects with one or more absolute contraindications to thrombolytics and whose initial treatment plan includes FlowTriever are allocated to the Contraindication Cohort. Subjects without any absolute contraindications (whether there are relative contraindications to thrombolytics or no contraindication to thrombolytics) are allocated to the RCT Cohort.

Study sites will receive the subject randomization assignment electronically in the electronic data capture (EDC) system upon completion of baseline information used to stratify randomization using the calculated VTE-BLEED score. Subjects will be randomized to and treated with (a) mechanical thrombectomy with FlowTriever or (b) catheter-directed thrombolysis per local practice standards.

INDEX PROCEDURE

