ICU	Intensive Care Unit
ISTH	International Society on Thrombosis and Haemostasis
ITT	Intention To Treat
LMWH	Low molecular weight heparin
LV	Left ventricle
mMRC	Modified Medical Research Council Dyspnea Scale
PA	Pulmonary Artery
PE	Pulmonary Embolism
PEmb-QOL	Pulmonary Embolism Quality of Life
PESI	Pulmonary Embolism Severity Index
PP	Per Protocol
RV	Right ventricle
RV/LV	Right ventricular to left ventricular diameter ratio
sPESI	Simplified Pulmonary Embolism Severity Index
VTE	Venous thromboembolism

PROPRIETARY AND CONFIDENTIAL

The information contained in this document is the sole property of Inari Medical

	PEERLESS Study: Statistical Analysis Plan	Version 5.0 March 22, 2024 Page 8 of 25
---	--	---

1. Description of Study Objectives

The primary study objective is to compare the clinical outcomes of patients treated with the FlowTriever (FT) System versus catheter-directed thrombolysis (CDT) for use in the treatment of acute pulmonary embolism (PE).

2. Study Design

The PEERLESS study is a prospective, multicenter, open-label, randomized controlled trial of the FlowTriever System compared to CDT for acute PE, and includes a non-randomized cohort for subjects with an absolute contraindication to thrombolytics. The study will collect data on demographics, comorbidities, details from the PE diagnosis and treatment, and clinical outcomes through 30-day follow up. The follow up evaluations will include the 24-hour visit (24 hours \pm 8 hours), hospital discharge, and the 30-day/Exit visit (30 days +15 days). All windows reference time from Index Procedure completion (defined as time of exit from the procedure room).

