2.1. Study Population

Randomized Controlled Trial Cohort (RCT Cohort):

Up to 550 subjects with acute PE will be enrolled and randomized at up to 60 study sites in US, EU, and/or UK. All subjects who sign informed consent and who meet all of the inclusion criteria and none of the exclusion criteria will be randomized (1:1, FlowTriever or CDT). The inclusion and exclusion criteria are described in sections 2.3 and 2.4.

- One-to-one (1:1) randomization will be stratified by bleeding risk, as measured by the VTE-BLEED score¹. The detailed algorithm for computing VTE-BLEED score is described in Table 1 of the study protocol.
- Stratification by the VTE-BLEED algorithm will occur automatically in the Electronic Data Capture (EDC) system upon data entry, and randomization will be assigned accordingly.

Non-Randomized Absolute Contraindication to Thrombolytics Cohort (Contraindication Cohort):

Up to 150 additional subjects who meet study eligibility criteria and who have an absolute contraindication to thrombolytics, whose initial planned primary treatment strategy includes FlowTriever, will be evaluated as part of the Contraindication Cohort. The same RCT Cohort clinical assessments and follow up schedule will be administered in this Contraindication Cohort.

PROPRIETARY AND CONFIDENTIAL

The information contained in this document is the sole property of Inari Medical

	PEERLESS Study: Statistical Analysis Plan	Version 5.0 March 22, 2024 Page 9 of 25
---	--	---

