2.2. Point of Enrollment

To participate in the study, the patient must sign the informed consent. If a subject signs the informed consent but is later deemed NOT to meet the invasive systolic PA pressure eligibility criteria, the subject would be considered a screen failure and not enrolled in either the RCT Cohort or the Contraindication Cohort. Screen failures will be tracked in the EDC system with rationale for the screen failure. The point of enrollment is when the subject meets all eligibility criteria and study device enters the subject's body. If the index catheter-based intervention procedure is aborted before treatment catheter insertion or is not performed, the subject is considered a screen fail.

Enrollment considerations in study design

Any patient with a documented ***absolute contraindication*** to thrombolytics will be excluded from the RCT Cohort but may be enrolled in the Contraindication Cohort if treated with FlowTriever. Absolute contraindications include (per ESC Guidelines 2019² and AHA Scientific Statements 2019):

- History of hemorrhagic stroke or stroke of unknown origin
- Ischemic stroke in previous 6 months
- Presence of intracranial conditions that may increase the risk of bleeding, such as neoplasms, arteriovenous malformations, or aneurysms
- Recent (within 3 months) intracranial or intraspinal surgery or serious head trauma
- Bleeding diathesis
- Active internal bleeding, excluding menses
- Aortic dissection
- Severe uncontrolled hypertension
- Any other condition listed as an absolute contraindication on the product label for the thrombolytic agent planned for use by local standard and investigator discretion

Subjects with a ***relative contraindication*** to thrombolytics are eligible for the RCT Cohort per protocol. Subjects with only relative contraindication(s) to thrombolytics are not eligible for the Contraindication Cohort. Relative contraindications include:

- Transient ischemic attack in previous 6 months
- Oral anticoagulation, except for aspirin
- Therapeutic LMWH within 24 hours
- Pregnancy or first post-partum week
- Non-compressible puncture sites
- Traumatic resuscitation, defined as prolonged (>10 min) cardiopulmonary resuscitation

[figure not shown]
PROPRIETARY AND CONFIDENTIAL

The information contained in this document is the sole property of Inari Medical

- Refractory hypertension (systolic BP >180 mmHg or diastolic BP >110 mmHg) on two confirmed measurements
- Advanced liver disease

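### SAP 3.1's ITT set depends on treatment and data after an open-label randomisation; no all-randomised set is defined and no set is named as deciding the primary test

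*SAP*

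**What the plan says.** SAP 3.1 starts from everyone eligible, consented and randomised, then adds conditions that act later: "To be included in ITT, subjects must receive some treatment for PE after randomization", and "Subjects will be excluded from ITT population if no treatments were given, or no data were available after randomization". The same section also says: "This study will consist of up to 550 subjects with acute PE who meet the eligibility criteria, and are enrolled, consented, and randomized".

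Enrolment has its own definition in SAP 2.2: "The point of enrollment is when the subject meets all eligibility criteria and study device enters" the body. SAP 2.2 continues: "If the index catheter-based intervention procedure is aborted before treatment catheter insertion or is not performed, the subject is considered a screen fail". Protocol 7 (Withdrawals and Lost to Follow up) repeats that rule.

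On timing and blinding, Protocol 7 (Allocation and Randomization) says: "Study sites will receive the subject randomization assignment electronically", once the baseline information used for stratification is complete. SAP 2 says: "The PEERLESS study is a prospective, multicenter, open-label, randomized controlled trial".

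SAP 3 defines three populations: ITT, per protocol (PP, a subset of ITT) and the Contraindication Cohort. Protocol 10 leaves the choice of population to the SAP. SAP 3.2, 5.2 and 5.3 run the primary test in both ITT and PP. The only guidance on reading the two results is that agreement is taken as a sign of robustness.

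**The concern.** An ITT analysis is protected because membership is fixed at randomisation. Here membership depends on what happens after staff know the arm. A site could be readier to go ahead with one assigned therapy than with the other, for sicker or for healthier patients. Subjects whose procedure is then not done may disappear from the analysis, and the arms are no longer comparable. PP cannot repair this, because it is drawn from the same reduced set. With two sets tested and neither ranked, the plan also has no answer if one is significant and the other is not.

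**Working it through.** **1. Can a subject leave after assignment is known?** The documents point both ways.
- SAP 2.1 and Protocol 6 say that subjects "who meet all of the inclusion criteria and none of the exclusion criteria will be randomized". Invasive PA pressure is exclusion 9, so this can be read as placing every eligibility check before randomisation.
- The Protocol synopsis speaks of baseline inclusion criteria. Protocol 7 issues the assignment on baseline data and takes the PA pressure just before the therapeutic catheter goes in. That reads as randomisation first.
- The enrolment flowcharts are not shown in the text available, so they cannot settle the order.
- The screen-fail rule for a procedure that is not performed is not tied to any eligibility criterion, so it can act after assignment on either reading.

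**2. Which randomised subjects are kept?**

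| Randomised subject | SAP 3.1 | SAP 2.2 / Protocol 7 |
|---|---|---|
| Study device entered, data present | In | Enrolled |
| PE treatment but no catheter procedure | In, if 'some treatment' is read broadly; unclear if 'enrolled' is a condition | Screen fail |
| No PE treatment | Out | Screen fail |
| Study device entered, no data afterwards | Out | Enrolled |

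The second row is the conflict.

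**3. Could the missing subjects be restored at analysis?** SAP 2.2 and Protocol 6 say that screen failures are tracked with the reason. The assessment schedule (Protocol 7) covers enrolled subjects, and adverse-event collection (Protocol 9) starts after enrolment. No collection of outcomes for screen fails is described.

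**4. The plan's own figure.** The 432 in SAP 5.1 cannot be reproduced, because neither document gives component rates. Back-solving with N = σ²(1.960 + 0.842)²/ln(WR)² and σ² = 4(1+p)/[3 × 0.25 × (1−p)], where p is an assumed share of ties:
- p = 0.1: σ² = 6.52, win ratio 1.41.
- p = 0.5: σ² = 16, win ratio 1.72.

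The step to 550 allows 1 − 432/550 = 21.5% loss. Changing the analysis set alters neither number.

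**5. Size of the no-procedure route.** SAP 5.2 statistic: z = T/√V, V = n_FT·n_CDT/[N(N−1)]·ΣU_i², reject if z > 1.96. There were 275 per arm, identical true outcomes in both arms and 100,000 replicates (Monte Carlo SE about 0.0005). A share q of subjects is prone to no procedure and is lost. All rates are assumed:

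| Group | Death / ICH / major bleed / deterioration or bailout | ICU none / ≤24 h / >24 h |
|---|---|---|
| Usual | 1 / 0.5 / 5 / 5% | 40 / 30 / 30% |
| Prone, strongly poor prognosis | 10 / 2 / 12 / 25% | 10 / 20 / 70% |
| Prone, mildly poor | 3 / 1 / 7 / 12% | 30 / 30 / 40% |
| Prone, good | 0.3 / 0.1 / 2 / 2% | 70 / 20 / 10% |

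One-sided type I error at q = 2 / 4 / 8% (about 5-6, 11 and 22 subjects of 275):

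| Who is lost | Strongly poor | Mildly poor | Good |
|---|---|---|---|
| FlowTriever only | 0.041 / 0.067 / 0.146 | 0.030 / 0.036 / 0.052 | 0.017 / 0.012 / 0.006 |
| CDT only | 0.014 / 0.008 / 0.002 | 0.021 / 0.017 / 0.011 | 0.035 / 0.049 / 0.082 |
| All prone in FlowTriever, half in CDT | 0.033 / 0.043 / 0.068 | 0.028 / 0.030 / 0.037 | 0.021 / 0.017 / 0.012 |
| Both arms equally | 0.024-0.026 | 0.024-0.026 | 0.024-0.026 |

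Removing instead the 6 FlowTriever subjects who actually ranked worst gave 0.068-0.075. That is a ceiling, since outcomes are unknown when a procedure is cancelled.

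**6. The no-data clause alone.** A subject kept with every pair unsettled has U_i = 0 and adds nothing to T, ΣU_i² or the win ratio. Only the factor in V moves. For 11 such subjects in one arm it goes from 275 × 264/(539 × 538) = 0.25036 without them to 275 × 275/(550 × 549) = 0.25046 with them. The ratio is 1.0004 and its square root 1.0002, so z changes by about 0.02%.

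**7. How far the repair goes.** Keep FlowTriever-only non-performers with tiers 1-4 known and the ICU tier unsettled, at q = 2 / 4 / 8%. The error is 0.032 / 0.039 / 0.058 (strongly poor), 0.027 / 0.031 / 0.035 (mildly poor) and 0.018 / 0.014 / 0.008 (good). One time origin with all tiers observed in both arms gives 0.024-0.026.

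**The case against.** The best defence is that SAP 3.1 asks only for some PE treatment, not the assigned therapy. The Protocol's background calls anticoagulation the mainstay of therapy, and inability to anticoagulate is an exclusion. Almost every eligible inpatient would then qualify, and the sentence about 550 subjects merely states the study's size. This stands as a plausible reading. It does not settle the matter, because SAP 3.1 does not say that anticoagulation counts, and SAP 2.2 and Protocol 7 still remove the same subject as a screen fail.

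Second, the type I figures size the screen-fail rule under assumed, one-sided, informative loss, and not the quoted sentence. That stands. If all eligibility checks precede randomisation, little discretionary time may remain after assignment. The 72-hour limit runs from diagnosis or arrival, so it does not measure that gap.

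Third, ITT's priority is implied: it is listed first, PP is its subset, and poolability is assessed in ITT only. This is fair, but an implication is weak ground for the one test that decides the trial.

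Fourth, untreated subjects do not fit the endpoint definitions. Deterioration must be new relative to enrolment, catheter-based or lytic bailout must follow the start of the assigned therapy, and ICU time runs from the end of the procedure or a later ICU admission. This stands and limits what the fix can do.

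A reader might also infer that the PP list deletes bailout events. SAP 3.2 permits that but does not require it, a crossover-only reading is natural, and ITT still reports those events. It is a minor wording matter and carries no weight here.

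**Conclusion.** The point holds as a defect of definition. The set called ITT is a modified ITT, the rules conflict on randomised subjects without a catheter procedure, no all-randomised set exists, and no set is named as deciding. Bias requires that non-performance after assignment differ by both arm and prognosis. With 2% of one arm lost, the assumed rates give a one-sided type I error of about 0.014 to 0.041 against 0.025, depending on which arm and which patients; equal loss gives none.

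A reader might infer that the plan favours FlowTriever, or that the error will reach 0.146. The documents support neither. They give no rate of non-performance and no direction, and 0.146 needs about 22 strongly poor-prognosis subjects lost from one arm and none from the other. Nor does the no-data clause by itself distort the test. The figures show sensitivity and do not predict what will happen.

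**What to change.** 1. Define ITT as all randomised eligible subjects, analysed as assigned, whether or not the procedure was performed. Name it as the set that decides the primary F-S test. Reconcile SAP 2.2 and Protocol 7 with SAP 3.1 so that a randomised subject is not reclassified as a screen fail. State whether the PA-pressure check comes before or after randomisation. If after, subjects failing that objective pre-device criterion may be excluded in both arms, with counts by arm and a sensitivity analysis that includes them.

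2. For randomised subjects without an index procedure, collect in-hospital vital status, ICH and major bleeding by chart. State one time origin for them and disclose that it differs from that of treated subjects. Treat the tiers that are undefined without a procedure (deterioration or bailout, and ICU stay) as unsettled under SAP 5.2, with the multiple imputation of SAP 4 as sensitivity. Say openly that this reduces the bias without removing it. The partial recovery in step 7 of the working assumed tier 4 known; leaving tier 4 unsettled as well was not simulated and will probably recover less. A common-origin analysis from randomisation is optional, because it needs pre-procedure data in treated subjects.

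3. Keep the present set as a named modified-ITT sensitivity analysis, report PP as supportive, and list all post-randomisation exclusions with reasons by arm. As a minor clarification, say whether the PP exclusion for other PE treatments means initial therapy only.

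Cost: SAP wording, a short protocol amendment, a few chart reviews if the consent covers them, and slight dilution of the effect. The 432 and 550 do not change.

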3.2. Per Protocol Population

Per Protocol (PP) population is a subset of ITT population that adhere to the protocol. The following are some of the possible reasons to exclude subjects from PP population.

- Non-compliant
- Protocol deviations
- Withdrawn from study
- Received other PE treatments than the assigned

The primary and secondary endpoints will be analyzed separately for both ITT and PP populations.

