- Requirement for an increase in fraction of inspired oxygen requirements 0.20 or greater, lasting longer than 30 minutes (e.g. from 0.21 to 0.41)
- Need for intubation in a previously non-intubated subject, or unplanned use of extracorporeal membrane oxygenation (ECMO)

Note that transient fluctuations in hemodynamic and/or respiratory function may be common during thrombectomy and thrombolysis procedures, and events not meeting both severity and duration requirements are not considered meeting the definition of Clinical Deterioration. Such changes may resolve spontaneously upon continuation of an existing treatment plan, and as such are unremarkable. Vagal episodes are also, in themselves, not considered Clinical Deterioration. Shorter term changes in hemodynamic or respiratory function, when accompanied by an unplanned escalation of therapeutic measures under the primary clinician's judgement to avoid overt deterioration, may be considered Bailout Therapy. Any such escalations of therapy will be documented in detail and adjudicated by a Clinical Events Committee (CEC).

Bailout Therapy is an unplanned escalation of therapeutic measures, taken when the patient's condition has not improved or is not improving according to expectations. Potential Bailout Therapy events will be adjudicated by a Clinical Events Committee, including when any of the following occur:

- Unplanned use of additional mechanical, pharmacomechanical, pharmacologic catheter-based therapies, or systemic thrombolytics, or changing from the assigned treatment strategy, after initial treatment strategy as assigned was initiated.
 - If catheter-directed thrombolysis (CDT) was the assigned treatment strategy and emergent/clinically driven systemic thrombolytic administration (e.g. ≥ 10 mg tPA) was required after CDT was initiated, this would be considered a bailout.
 - If the length of thrombolytic administration is simply extended and is not emergent or clinically driven, this would not qualify as a bailout.
 - If mechanical thrombectomy was the assigned treatment strategy, low-dose catheter-directed **adjunctive** thrombolytic therapy (less than 10 mg tPA) that is administered intra-procedurally or post-procedurally will be *strongly discouraged* but not considered a bailout
- Surgical thrombectomy

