Before escalating to a Bailout Therapy, physicians are encouraged to consider the patient's condition and identify one or more reasons from the following list to justify the need for Bailout Therapy. These reason(s) will be documented in the study case report forms (CRFs).

- Persistent elevated respiratory rate
- Ongoing or increased requirement for supplemental oxygen
- Persistent or new-onset tachycardia
- Sustained or sudden bradycardia
- Sudden or persistent hypotension, not associated with a vagal episode, or signs of end-organ hypoperfusion
- Hemodynamic worsening or lack of hemodynamic improvement
- Lack of improved lung perfusion, or inadequate clot resolution
- New-onset, persistent, or worsening symptoms of PE

Any unplanned escalation of therapy adjudicated by the CEC to not meet clinical definitions for Bailout Therapies will be considered a protocol deviation.

Definition of ICU Admission and ICU Length of Stay

ICU Admission will be defined as admission or transfer to an Intensive Care Unit (ICU), Critical Care Unit (CCU), or similar high-acuity floor, collectively referred to as “ICU.” For the purpose of the endpoint assessment, ICU Admission is met under the following conditions:

- Orders are entered for Subject to be admitted or transferred to the ICU after the end of the Index Procedure and before hospital discharge from the index hospitalization, up to a maximum of 7 days from the end of the Index Procedure, or
- Subject had been in the ICU leading up to the Index Procedure, with plans to return to the ICU immediately after the end of the Index Procedure, with or without a transfer to a PACU, recovery room, or similar temporary step-down unit according to local standard.

ICU Length of Stay (LOS) is the total number of hours a subject is medically required to be in the ICU, measured from the end of the Index Procedure or the time of ICU Admission, whichever is later, until the time of an *order to discharge* the subject from the ICU or transfer the subject to a standard or lower-acuity unit. If a subject remains physically located in the ICU due to hospital bed availability, transport delays, or other non-medical reasons instead of a need for high acuity of care, the time of the order for discharge or transfer, rather than the actual time a subject physically leaves the ICU, is used for assessing ICU LOS.

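### SAP 3.2 lets the per-protocol population drop subjects whose adjudicated bailout used a different treatment, so it can be selected on part of tier 4, which it then analyses

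*SAP*

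**What the plan says.** SAP 3.2 begins with a general rule: "Per Protocol (PP) population is a subset of ITT population that adhere to the protocol". It then lists some possible reasons for exclusion, one of which is "Received other PE treatments than the assigned". That bullet has no timing limit and no exception for endpoint events. The same section adds: "The primary and secondary endpoints will be analyzed separately for both ITT and PP populations".

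SAP 2.5 makes tier 4 of the primary endpoint "Clinical deterioration defined by hemodynamic or respiratory worsening, and/or escalation to a bailout therapy". The same item is in the four-component composite (SAP 5.4.1) and has its own Fisher test (SAP 5.4.6).

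Protocol section 5 says that potential bailouts, which the CEC adjudicates, include "Unplanned use of additional mechanical, pharmacomechanical, pharmacologic catheter-based therapies, or systemic thrombolytics". Surgical thrombectomy is also on the list, and so is "changing from the assigned treatment strategy, after initial treatment strategy as assigned was initiated". The section also says which escalations count as non-adherence: "Any unplanned escalation of therapy adjudicated by the CEC to not meet clinical definitions for Bailout Therapies will be considered a protocol deviation".

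SAP 5.3 and 5.4.1 read similar ITT and PP results as evidence that the treatment effect is robust.

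**The concern.** A subject who starts FlowTriever and then needs systemic lysis, or who starts CDT and then needs mechanical thrombectomy, has received PE treatment other than the assigned one. On the plain words of SAP 3.2 that subject may be left out of PP. Under the protocol the same subject has had a tier-4 event and, once the CEC accepts the bailout, is not called a deviation.

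If the bullet is applied this way, PP is defined by a post-randomisation outcome that it goes on to test. The excluded subjects' deaths, bleeds and ICU stays leave with them. Agreement between ITT and PP would then partly reflect which outcome events had been removed, and would be weak support for the robustness statement. The trial is open-label and the list of reasons is open-ended, so a fixed rule is worth having.

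**Working it through.** **Texts side by side.**

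- Protocol section 5: bailout happens after the assigned strategy has been started; CEC-accepted bailout is an outcome; only CEC-rejected escalation is a deviation.
- SAP 3.2: receipt of other PE treatment, at any time and for any reason, may exclude.
- I found no text in either document that carries the protocol's distinction into the PP definition.

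**Which subjects are exposed.** Those whose bailout used a different modality. Bailout with more of the assigned modality is arguably not other treatment, and deterioration without added PE therapy stays in PP.

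**Size.** The SAP's 432 subjects (216 per arm) cannot be reproduced, because neither document gives component rates, and this point does not affect it. All rates below are therefore assumptions:

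- both arms: death 1%, ICH 0.5%, major bleeding 6%, deterioration d = 2%
- bailout b, FlowTriever v CDT: 2% v 1% to 4% v 1%
- components independent, as in the SAP's own sample-size simulation

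Tier-4 rate:

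- ITT: 1 − (1 − d)(1 − b)
- all bailouts removed: d
- half removed in each arm: the same formula with b′ = (b/2)/(1 − b/2)

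At each tier, P(win) = q_C(1 − q_F) and P(loss) = q_F(1 − q_C), weighted by the probability that all higher tiers tie.

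*Four components, 4% v 1%.*

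- Tiers 1 to 3, wins (losses equal): 0.0099 + 0.9802 × 0.004975 + 0.9704 × 0.0564 = 0.0695. Probability of a tie through tier 3: 0.9802 × 0.99005 × 0.8872 = 0.8610.
- ITT tier 4: 1 − 0.98 × 0.96 = 5.92% v 1 − 0.98 × 0.99 = 2.98%. P(win) = 0.0695 + 0.8610 × 0.0298 × 0.9408 = 0.0936. P(loss) = 0.0695 + 0.8610 × 0.0592 × 0.9702 = 0.1190. Ratio 0.79.
- Half removed: b′ = 0.0204 v 0.0050, tier 4 = 4.0% v 2.5%. P(win) 0.0901, P(loss) 0.1031, ratio 0.87.
- All removed: tier 4 = 2.0% v 2.0%, ratio 1.00.

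*Five tiers, equal ICU (none / 0–24 h / >24 h = 35/30/35%), 4% v 1%.* The tie through tier 4 is 0.8610 × (1 − 0.0280 − 0.0574) = 0.7874. ICU adds 0.7874 × 0.3325 = 0.2618 to wins and to losses, giving 0.3555 / 0.3808 = 0.93.

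| Win ratio, 2% v 1% to 4% v 1% | ITT | PP, half removed | PP, all removed |
|---|---|---|---|
| Four components | 0.92 to 0.79 | 0.95 to 0.87 | 1.00 |
| Five tiers, equal ICU | 0.98 to 0.93 | 0.99 to 0.97 | 1.00 |
| Five tiers, ICU favouring FlowTriever (45/35/20 v 30/35/35%) | 1.53 to 1.44 | 1.56 to 1.51 | 1.60 |
| Four components, major bleeding 4% v 7% | 1.24 to 1.04 | not computed | 1.43 |

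The 1.00 entries follow by construction, because bailout is the only difference between arms in those rows. The last two rows show that the shift does not depend on this. Reversing the bailout gap moves ITT to the other side: four components 1.09 to 1.27, five tiers with equal ICU 1.02 to 1.07.

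**Removal that differs by arm.** Four components, 4% v 1%, ITT 0.79:

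- Only CDT bailouts removed (tier 4 5.92% v 2.0%): (0.0695 + 0.8610 × 0.02 × 0.9408) / (0.0695 + 0.8610 × 0.0592 × 0.98) = 0.0857 / 0.1195 = 0.72. The gap widens.
- Only FlowTriever bailouts removed (2.0% v 2.98%): (0.0695 + 0.8610 × 0.0298 × 0.98) / (0.0695 + 0.8610 × 0.02 × 0.9702) = 0.0947 / 0.0862 = 1.10. The direction reverses.

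**Second check.** A simulation with 275 per arm, 1,500 replicates and other assumed rates (death 0.5%, ICH 0.5%, major bleeding 5%, deterioration 3%, ICU 30/30/40%) agrees. With bailout 5% v 2%, the five-tier ratio is 0.93 with bailouts kept and 1.00 with all dropped; the four-component ratio is 0.80 and 1.01. With 5% in both arms the ratios stay near 1.00, but the tier-4 rate falls from 7.9% to 3.0% in each arm.

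**The case against.** The strongest reply is that the documents nearly answer the point already. The opening sentence of SAP 3.2 makes adherence the test, the bullets are only possible reasons, and Protocol section 5 does not class adjudicated bailout as a deviation. The bullet also reads naturally as crossover at the start of treatment. Such subjects can exist, because SAP 3.1 says "To be included in ITT, subjects must receive some treatment for PE after randomization" and does not require the assigned treatment. This is a sensible reading and may be the intended one, but the SAP does not state it and the bullet's words reach further.

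The second reply is size, and most of it stands. The 1.00 figures need every bailout to be removed, which the SAP neither requires nor, for same-modality bailout, clearly permits. With half removed at 2% v 1%, the five-tier ratio moves only from 0.977 to 0.988. The nearest figures in the protocol are 2 of 106 FLARE subjects given thrombolytics (1.9%) and a 5.9% procedural failure rate in a 34-patient series of sicker patients. Neither uses this trial's bailout definition. The first lies nearest the mildest scenario.

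A reader might also infer that PP always shrinks a bailout difference, or that it favours FlowTriever. Neither follows. Removal may depend on the therapy used and so differ by arm, and the documents give no bailout rates from which to predict a direction.

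**Conclusion.** The point holds as a defect in the PP definition. Applied literally, SAP 3.2 selects PP on part of tier 4. The between-arm bailout difference is then lost if all bailouts are removed, shrunk if equal fractions are removed in both arms, and possibly distorted in either direction otherwise. On the assumed rates the effect is modest for the five-tier primary endpoint and larger for the four-component composite and the tier-4 test. With equal bailout rates and equal removal, the win ratio barely moves.

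A reader might go further and infer that the SAP requires bailout subjects to be excluded, or that the primary result is biased. The documents do not support either: the list gives possible reasons only, and the ITT analysis keeps these subjects and their events. SAP 5.3 sets no success rule that turns on PP. What is weakened is the PP result and the robustness reading placed on its agreement with ITT. The SAP should be corrected, but the trial's main analysis does not depend on it.

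**What to change.** Add one sentence to SAP 3.2: CEC-adjudicated bailout after the assigned treatment was started is an endpoint event and is not by itself a reason for PP exclusion; such subjects stay in PP with the bailout counted in tier 4.

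Leave the bullet otherwise as it is. Limiting it to subjects who never started the assigned treatment would be too broad. It would also stop the bullet from covering adjunctive lytic in FlowTriever subjects, which the protocol discourages but does not count as bailout. CEC-rejected escalations can still be handled as deviations.

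The cost is one sentence and no new data, since bailout is already adjudicated. The downside is that PP becomes somewhat less distinct from ITT.
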